### **Surrogate Primary Endpoint for Patients with Late-stage HAT**

Amendment 2 dated 07/01/2020 deletes analysis of the surrogate primary endpoint at 12 months in patients with late-stage g-HAT, as the data set required for early submission at 12 months is not available in its entirety.

#### **2.2.2. Secondary Endpoints - Efficacy**

##### **Efficacy in Patients with Late-stage HAT**

A patient with late-stage HAT will be considered as a success at 6 months and at 12 months if the CSF WBC is equal to or below 20/ $\mu$ L and in the absence of trypanosomes, rescue treatment and signs or symptoms suggesting a relapse at the visit in question or previously.

If the patient does not have a lumbar puncture at 6 months, the outcome of the lumbar puncture at 12 months will be used. If the patient does not have a lumbar puncture at 12 months and if a lumbar puncture is performed at 18 months, the outcome at 18 months will be used. Otherwise, the outcome at 6 months will be used. If the patient has no post-treatment lumbar puncture, s/he will be considered as a failure. Patients lost to follow-up and deaths, regardless of the cause, will be considered as failures.

##### **Endpoints in Patients with Early- or Intermediate-stage HAT**

Two efficacy endpoints will be used for patients with early- and intermediate-stage HAT: the outcome at 12 months and the outcome at 18 months after receiving treatment. A patient will be considered as a success at 12 months if the patient is alive with no evidence of trypanosomes in any body fluid and if the CSF

WBC is equal to or less than 20/ $\mu$ L. A patient with no parasitological evidence of relapse, but with a CSF WBC above 20/ $\mu$ L or who, in the Investigator's opinion, requires rescue treatment, will be considered as a relapse. A patient who refuses the lumbar puncture at 12 months will be classified as a probable cure (success) in the absence of any clinical signs or symptoms suggestive of THA or with another obvious aetiology, provided that the outcome was favourable, i.e. a CSF WBC equal to or less than 5/ $\mu$ L, at 6 months. Death for any reason, patients lost to follow-up and not retrieved or patients with no post-treatment lumbar puncture will be considered as failures, with the exception of patients who fled the region due to armed conflict or natural disaster. For memory, patients who fled the region due to armed conflict or natural disaster will not be included in the mITT population and will therefore not be taken into account in the calculation of the success rate. A patient with early- or intermediate-stage HAT will be considered as a **success** at 18 months if the CSF WBC is equal to or below 20/ $\mu$ L and in the absence of trypanosomes, rescue treatment and signs or symptoms suggestive of a relapse. If the patient does not have a lumbar puncture at 18 months, the outcome at 6 months or at 12 months will be used.

A patient with early- or intermediate-stage HAT will be considered as a success at 6 months and at 12 months if the CSF WBC is equal to or less than 20/ $\mu$ L and in the absence of trypanosomes, rescue treatment and signs or symptoms suggestive of a relapse. If the patient does not have a lumbar puncture at 6 months, the outcome at 12 months and, if necessary, at 18 months will be used. If the patient does not have a lumbar puncture at 12 months, the outcome at 18 months will be used and, if necessary, the outcome at 6 months will be used. If no post-treatment lumbar punctures were performed, the outcome will be considered as unfavourable.

### **2.2.3. Secondary Endpoints - Safety**

The secondary endpoints concerning the safety of acoziborole are as follows:

- Occurrence of any AE, including an abnormal laboratory test result, during the observation period. AEs will be graded according to the Common Toxicity Criteria for Adverse Events (CTCAE) of the National Cancer Institute (NCI), version 4.03 (16).
- Occurrence of any SAE during the observation period and until the end of follow-up (18 months).

### **2.2.4. Secondary Endpoints - Pharmacokinetics**

The following PK parameters will be measured in the blood and CSF:

- Concentrations of acoziborole in whole blood and CSF, and population PK parameters, i.e. clearance, AUC and half-life (see also Section 6.3.3 Pharmacokinetic Analyses; p43)

### **2.2.5. Secondary Endpoints - Electrocardiogram**

ECG tracings will be recorded at various timepoints to assess the QT/QTcF interval and variations over time (see Section 6.3.2 Digital ECG; p42 and the Schedule of Procedures; p89).

## **3. Study Design**

This is a multicentre, prospective, open-label, non-randomised, phase II/III study to assess the efficacy and safety of acoziborole in two cohorts of patients with g-HAT. The first cohort will be composed of patients with late-stage HAT, and the second cohort will be composed of patients with early- or intermediate-stage HAT.

Early- and intermediate-stage patients will be enrolled in the same centres as late-stage patients, however enrolment of early- and intermediate-stage patients will begin approximately 6 months later, once the Data and Safety Monitoring Board (DSMB) has examined the PK and safety data at 3 months for the first 20 patients with late-stage HAT and once it has been informed of the results of the first futility analysis.

## **4. Selection of Study Population**

The patient must fulfil all of the inclusion criteria and none of the exclusion criteria. The inclusion and exclusion criteria are similar to those in the study published by Priotto et al. (18), and the study design is the same as that in the study conducted by WHO-TDR and in the DNDiHATFEX004 study, as these three studies constitute the basis for the use of NECT as a yardstick in this study. Once the patient has signed the informed consent form, s/he will be assigned a number comprising the 3-digit centre number starting with 7 (7XX- and a 3-digit patient

number, which the Investigator will assign in ascending order of inclusion of the patient in the study.

#### **4.1. Enrolment and Inclusion Procedures**

The study is to be conducted in hospitals located in endemic regions and having experience in treating patients with HAT.

In Guinea, the clinical study will be conducted in the HAT treatment centre in Dubreka. The HAT treatment centre in Forecariah and the prefectoral hospital in Boffa will be satellite centres whose role will be to screen patients and refer them to the centre in Dubreka. Follow-up visits may take place in the centres in Forecariah and Boffa with the National Investigator and her/his team, who will travel to the centres to ensure better patient follow-up and avoid patients lost to follow-up.

Patients who meet pre-inclusion criteria that do not require any study-specific procedures will be invited to participate in the study, and they will then receive the information necessary to collect their informed consent.

For the patient to be enrolled in the study, s/he must sign the informed consent form after having received explanations from the Investigator or a representative. The patient will then be considered as a “screened patient”.

The enrolment and inclusion procedures are to be performed between 1 and 15 days prior to the planned date of administration of acoziborole. The procedures are described in Section 6, Schedule of Study Procedures and Assessments; p39.

#### **4.2. Inclusion Criteria**

To be included in the study, the patient must fulfil all of the following criteria:

- Male or female
- 15 years of age or older
- Signed informed consent form (as well as assent from illiterate and under-age patients, and those unable to give consent)
- Karnofsky Performance Status above 50 (see Appendix 2; p83)
- Able to ingest oral tablets
- Having a permanent address or being traceable by other persons
- Able to comply with the schedule of follow-up visits and requirements of the study
- Agreement to be hospitalised in order to receive treatment.

For patients with late-stage HAT:

- Confirmation of g-HAT by detection of the parasite in the blood and/or the lymph and/or the CSF, at the investigational centre
- If trypanosomes are found in the blood or lymph, but not in the CSF, the CSF WBC, measured at the investigational centre, must be above 20/ $\mu$ L for the patient to be included in the cohort of patients with late-stage HAT

For patients with early- or intermediate-stage HAT:

- Confirmation of g-HAT by detection of the parasite in the blood and/or the lymph, at the investigational centre
- Absence of parasites in the CSF
- The CSF WBC, measured at the investigational centre, must be between 6 and 20/ $\mu$ L for the patient to be included in the cohort of patients with intermediate-stage HAT and equal to or below 5/ $\mu$ L for the patient to be included in the cohort of patients with early-stage HAT.

#### **4.3. Exclusion Criteria**

To be included in the study, the patient must not fulfil any of the following exclusion criteria:

- Severe malnourishment, defined as body-mass index (BMI) below 16
- Pregnancy or breastfeeding (for women of child-bearing potential, confirmed pregnancy on a urine pregnancy test performed within 24 hours prior to administration of acoziborole – see Section 5.2.3 Contraception; p36)
- Clinically significant medical condition that could, in the opinion of the Investigator, jeopardise the patient's safety or interfere with participation in the study, including, but not limited to significant liver or cardiovascular disease, suspected or proven active infection, central nervous system trauma or seizure disorder, coma or consciousness disturbances
- Severely deteriorated health status, e.g. due to cardiovascular shock, respiratory distress syndrome or end-stage disease
- Previously treated for HAT (except prior treatment with pentamidine)
- Prior enrolment in the study
- Foreseeable difficulty complying with follow-up, including migrant worker, refugee status, itinerant trader etc.
- Current alcohol abuse or drug addiction
- Not tested for malaria and/or not having received appropriate treatment for malaria (see Section 5.2.1 Malaria; p36)

- Not having received appropriate treatment for soil-transmitted helminthiasis (see Section 5.2.2 Helminthiasis; p36)
- Clinically significant abnormal laboratory values including:
  - AST and/or ALT more than 2 times the upper limit of normal (ULN)
  - Total bilirubin more than 1.5 ULN
  - Severe leukopenia at less than 2000/mm^3
  - Potassium below 3.5 mmol/L
  - Any other clinically significant abnormal laboratory value.

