	
 
▪ Absence of parasites in the CSF
 
▪ The CSF white blood cell count, measured at the investigational centre, must be between 6 and 20/<math>\mu</math>L for the patient to be included in the cohort of patients with intermediate-stage HAT and equal to or below 5/<math>\mu</math>L for the patient to be included in the cohort of patients with early-stage HAT
 
 
Exclusion Criteria
 
 
▪ Severe malnourishment, as defined by a body-mass index below 16
 
▪ Pregnancy or breastfeeding, (for women of child-bearing potential, confirmed pregnancy on a urine pregnancy test performed within 24 hours prior to administration of acoziborole)
 
▪ Clinically significant medical condition that could, in the opinion of the Investigator, jeopardise the patient's safety or interfere with participation in the study, including, but not limited to significant liver or cardiovascular disease, suspected or proven active infection, central nervous system trauma or seizure disorder, coma or consciousness disturbances
 
▪ Severely deteriorated health status, e.g. due to cardiovascular shock, respiratory distress syndrome or end-stage disease
 
▪ Previously treated for HAT (except prior treatment with pentamidine)
 
▪ Prior enrolment in the study
 
▪ Foreseeable difficulty complying with follow-up, including migrant worker, refugee status, itinerant trader etc.
 
▪ Current alcohol abuse or drug addiction
 
▪ Not tested for malaria and/or not having received appropriate treatment for malaria
 
▪ Not having received appropriate treatment for soil-transmitted helminthiasis
 
▪ Clinically significant abnormal laboratory value including: 
 
○ AST and/or ALT more than 2 times the upper limit of normal (ULN),
 
○ Total bilirubin more than 1.5 ULN,
 
○ Severe leukopenia at less than 2000/mm^3,
 
○ Potassium below 3.5 mmol/L,
 
○ Any other clinically significant abnormal laboratory value.
 
 
 

Investigational Product	
The investigational product (IP) is acoziborole, in 320-mg tablets, administered by the oral route to patients in the fasting state according to the following dosing regimen:
 
 
▪ 960 mg (3 tablets) in a single intake on Day 1.
 

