### **1.6. Pharmacokinetics and Metabolism In Healthy Volunteers**

A randomised, double-blind, placebo-controlled Phase-I study (6) was performed in healthy African male volunteers between 18 and 45 years of age in order to assess the safety, PK and pharmacodynamics (PD) of acoziborole after single ascending oral doses. A total of 128 subjects were included, 102 of whom received acoziborole, and 26 received placebo. The doses studied ranged from 20 mg to 1200 mg.

Acoziborole was rapidly absorbed in the healthy volunteers, and the plasma concentrations remained stable for at least 96 hours, indicating that the elimination half-life is relatively long. Analysis of the PK data showed that acoziborole undergoes extensive enterohepatic recycling. Activated charcoal was administered to subjects, generally starting on Day 5, in order to accelerate clearance of the product and shorten the follow-up period for the subjects. The therapeutic dose of 960 mg was also administered without activated charcoal to mimic the future conditions of administration to patients. Clearance of acoziborole from the body was very slow with a half-life of approximately 400 hours. This profile suggests that a single administration of acoziborole may be sufficient for the treatment of HAT. Inter-subject variability was low at approximately 20%.

Contrary to what was observed in animals, metabolism of acoziborole was very limited, which may explain the very long half-life in humans.

The unbound fraction was determined by ultrafiltration. The ultrafiltrate-to-plasma ratio was in the same range as that in the *in-vitro* study. The mean unbound fraction was 2.2% of the plasma concentration.

In addition, concentrations of acoziborole were determined in the CSF of healthy volunteers. In the 240 and 320 mg dose-level groups, mean CSF concentrations corresponded to 2.2% of the plasma concentration with a range of 1.8% to 3.2%.

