### **6.2.3. Baseline Assessment**

The baseline assessment will be performed between Day -4 and Day -1 to assess the patient's baseline status just prior to administration of the IP. The patient's eligibility to participate in the study will also be reconfirmed. The following procedures will be performed:

- Review of informed consent/assent;
- Review of Karnofsky performance status;
- Review of inclusion/exclusion criteria;
- Height, weight and BMI;
- Vital signs: body temperature, blood pressure, heart rate, respiratory rate and general status;
- Physical and neurological examinations; questionnaire on symptoms;
- Collection of concomitant medication and adverse events;
- Urine pregnancy test for women of child-bearing potential;
- Thyroid function test: TSH, free T3, free T4;
- Laboratory safety assessments, if the following tests were performed before D-4 during the Pre-screening / Screening period or if the tests found abnormalities requiring repeat tests – sampling will be performed in the morning on patients in the fasting state:

- Haemoglobin
- Haematology: WBC, platelet count
- Biochemistry: albumin, ALP, ALT, AST, BUN, chloride, creatinine, glucose, potassium, sodium, calcium, total bilirubin, bicarbonates and total protein.

If the assessments were performed within 4 days prior to administration of the IP, those findings will be considered as baseline values and recorded in the CRF.

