#### **6.3.4. Assessments on Day 1 - Treatment Day**

The following procedures will be performed on Day 1 (see also Table 6 - Schedule of Procedures; p89).

- Collection of concomitant medication;
- Collection of adverse events;
- Two duplicate ECGs and blood sampling for PK analyses prior to administration of acoziborole (cf. Table 3 and Table 4);
- Triplicate ECG and blood sampling for PK analyses after administration of acoziborole (cf. Table 3 and Table 4).

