### 6.5.8. Exposure *in utero*

At least five pregnancy tests are planned during the study: at the screening visit, at the baseline assessment (between Day -4 and Day -1), on Day 11 and at the

out-patient follow-up visits up to 6 months. Among women of child-bearing potential, only those who have a negative result on the pregnancy test at the baseline assessment will be eligible to participate in the study.

Pregnancy is not considered to be an AE.

The Investigator must report any pregnancy using the appropriate pregnancy reporting form (see Investigator Manual). The pregnancy must be reported whether or not an AE occurred. If known, the due date should be specified.

The Investigator must monitor the patient until the full term of the pregnancy or preterm in the event of a miscarriage. The Investigator must provide information on the outcome of the pregnancy using the pregnancy follow-up reporting form.

A physician, preferably a paediatrician, should examine the newborn at birth and submit a report using a Newborn Follow-up form. The Investigator will offer the parents follow-up on infants exposed to the IP *in utero* until they reach 24 months of age. As far as possible, stillborn infants should be examined by a physician to ascertain the cause of death.

Any SAE that occurs in a pregnant patient (exposed to the IP or who is found to be pregnant any time up to the 6-month visit) and that concerns the pregnancy or the foetus, will be reported using the SAE reporting form in the same manner as any other SAE. Any non-serious AE concerning a pregnant patient will be collected using the AE form in the CRF.

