## Appendix 4 - Schedule of Events

**Table 6 - Schedule of Events**

Protocol procedures and forms to be completed	Pre-screening and screening	Baseline	Observation Period until End of Hospitalisation Visit (EOH)																
			D-15 to D-1	D-4 to D-1	D1	D2	D3	D4	D5	D6	D7	D8	D9	D10	D11	D12	D13	D14	
Timing →																			
Diagnosis, i.e. detection of parasite in blood and/or lymph	x														x				x (6, 12 & 18 months only)
Lumbar puncture (parasite and WBC in CSF)	x														x				x (6, 12 & 18 months only)
Informed consent	x	Check																	
Pre-treatment of helminthiasis (+ 3-day recovery period)	x																		
Rapid diagnostic test and/or thick blood smear for malaria	x																		
Pre-treatment of malaria as needed (+3-day recovery period)	x																		
Karnofsky index	x	Check																x	x
Urinary pregnancy test (only for women)	x	x												x				x (up to 6 months)	x
Inclusion/exclusion criteria	x	Check																	
Demographic data	x																		
Geographical data	x																		
Medical history, incl. symptoms, severity and time since start of disease	x																		
Weight, height and body-mass index	x	x						x						x			x	x	x
Vital signs 	x	x						x						x			x	x	x
Physical examination		x						x						x			x	x	x
Neurological examination		x						x						x			x	x	x
Haematology/biochemistry	x	x*						x						x			x	x	x
Thyroid function tests		x												x			x	x	x

Timing →	D-15 to D-1	D-4 to D-1	D1	D2	D3	D4	D5	D6	D7	D8	D9	D10	D11	D12	D13	D14	D15 (EoH)	3, 6, 12 and 18 months	Unscheduled visit 
ECG (2 duplicates) 			x																
ECG triplicate recording 			x	x	x	x	x						x						
Administration of SCYX-7158			x																
Collection of adverse events 	x	x	x	x	x	x	x	x	x	x	x	x	x	x	x	x	x	x	
Collection of concomitant medication	x	x	x	x	x	x	x	x	x	x	x	x	x	x	x	x (up to 6 months)		x	
Blood sampling for pharmacokinetic analyses 			x	x	x	x	x					x				x (up to 6 months)			
CSF sampling for pharmacokinetic analyses 												x							

\* If the tests were performed prior to D-4 in the Pre-screening/Screening Period or if the findings included abnormalities requiring repeat tests.

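### The exclusion criteria rely on a pregnancy test within 24 hours before dosing, but the visit schedule allows the last test from Day -4 to Day -1 and puts none on Day 1.

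*Protocol*

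**What the plan says.** The exclusion appears twice with the same limit. Protocol Section 4.3 relies on "confirmed pregnancy on a urine pregnancy test performed within 24 hours prior to administration of acoziborole", and the Protocol Summary gives it as "Pregnancy or breastfeeding, (for women of child-bearing potential, confirmed pregnancy on a urine pregnancy test performed within 24 hours prior to administration of acoziborole".

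The operational sections give a different timing:

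- Section 4.1: "The enrolment and inclusion procedures are to be performed between 1 and 15 days prior to the planned date of administration of acoziborole". It refers to Section 6 for the procedures.
- Section 6.2.3: "The baseline assessment will be performed between Day -4 and Day -1". This visit holds the last urine pregnancy test and the last review of the inclusion and exclusion criteria before treatment.
- Section 6.5.8 plans at least five tests, "at the screening visit, at the baseline assessment (between Day -4 and Day -1), on Day 11", and then at follow-up visits up to 6 months. It makes a negative baseline test a condition of eligibility and does not mention 24 hours.
- Section 6.3.4 lists for Day 1 only concomitant medication, adverse events, ECGs and PK sampling.
- Table 6 marks the pregnancy test at screening, baseline, Day 11, follow-up to 6 months and unscheduled visits. The criteria check is marked at baseline. Neither is marked on Day 1.

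Section 5.2.3, to which the exclusion criterion points, covers contraception and gives no test timing.

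**The concern.** The protocol sets a safety limit in its criteria and then gives sites a schedule that does not carry it out. A criteria review held on Day -4, Day -3 or Day -2 cannot confirm a test whose 24-hour window has not yet opened, and no later review is scheduled.

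The timing matters because exposure cannot be reversed. Treatment is one intake, and Section 1.6 reports: "Clearance of acoziborole from the body was very slow with a half-life of approximately 400 hours". Section 1.8 adds that plasma levels in healthy volunteers stayed above the effective concentration up to 69 days. Section 5.2.3 reports no preclinical effect on fertility or postnatal development, but also says the drug had not yet been given to women who could become pregnant. The test nearest to dosing is the last point at which exposure of a pregnancy can be prevented.

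There is a secondary effect on deviation handling. SAP Section 5 counts deviations that may significantly affect a patient's safety as major, and major deviations remove patients from the per-protocol set. A Day -4 test keeps to the Section 6 window but leaves the Section 4.3 test undone, so it is unclear how such a patient should be classified.

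**Working it through.** **1. Reproduce the planned number of tests.** Section 6.5.8 states at least five. From the schedule: screening (1) + baseline (1) + Day 11 (1) + Month 3 (1) + Month 6 (1) = 5. The figure is reached without a Day 1 test.

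**2. Age of the test at dosing.** SAP Section 7.5 confirms that there is no Day 0, so Day -1 is the calendar day before Day 1. At the same clock time:

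| Baseline test on | Hours before dose | Can meet 24 h? |
|---|---|---|
| Day -4 | 4 × 24 = 96 | No |
| Day -3 | 3 × 24 = 72 | No |
| Day -2 | 2 × 24 = 48 | No |
| Day -1 | 1 × 24 = 24 | Only if taken no earlier in the day than the dose |

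A Day -4 test is 96 / 24 = 4 times the limit. Even the end of Day -2 is at least 24 hours before any Day 1 dose, so three of the four permitted days are ruled out whatever the clock time.

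**3. Share of the baseline window that satisfies Section 4.3.** The window runs from the start of Day -4 to the end of Day -1, which is 96 hours. For a dose at clock hour *h* on Day 1, the part of the window within 24 hours of dosing is 24 − *h* hours. The documents give no dosing time. I assume 06:00 to 12:00. This fits the ECG and PK schedules, which label the 9-hour point as Day 1 and so imply a dose before about 24 − 9 = 15:00.

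- *h* = 6: (24 − 6) / 96 = 18 / 96 = 18.75%
- *h* = 12: (24 − 12) / 96 = 12 / 96 = 12.5%

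These are shares of calendar hours, not rates of non-compliance.

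**4. Number of women to whom the criterion applies.** Planned patients: 162 late-stage + about 50 early- or intermediate-stage = 212. The share of women of child-bearing potential is not given. Assuming 20% to 50%: 0.20 × 212 ≈ 42 and 0.50 × 212 = 106. This counts all women under the criterion, not those expected to be tested late.

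**The case against.** The strongest reply is that the two rules are compatible. Section 4.3 is binding, and the baseline window is a general one for a set of procedures. A test late on Day -1 satisfies both. Section 5.1.1 gives treatment only to patients who meet all criteria, and Section 6.2.3 requires those criteria to be reviewed, so dosing on a 96-hour-old test would be a deviation from Section 4.3. Section 6.5.8 makes a negative baseline test necessary, not sufficient, and its count of five is a minimum that leaves room for a repeat. Two tests precede dosing, contraception is advised and supplied free, and pregnancies are followed up. The Investigator Manual and CRF, which are not available here, may state the timing.

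Much of this stands. Compliance is possible, Section 6.5.8 does not override Section 4.3, and the missing documents may close the gap in practice. The documents also do not show how much detection differs between a test within 24 hours and one up to 96 hours before dosing.

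It does not remove the defect. A review held on Day -4, -3 or -2 cannot verify a test that is not yet due, and the schedule provides nothing afterwards to verify it. The other safeguards do not replace the check: the screening test may be up to 15 days old, the Day 11 test comes after exposure, and contraception does not detect an existing pregnancy.

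**Conclusion.** The concern holds. The protocol states the 24-hour limit twice, and no part of its visit schedule secures it. A site can follow Section 6 to the letter and give the dose on a test about 96 hours old. This conclusion rests only on the text and on calendar arithmetic. The 12.5% to 19% share of hours and the 42 to 106 women depend on the assumed dosing times and the assumed share of women, and the conclusion does not need them.

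This is an operational safety gap that should be corrected. It does not change the sample size or the primary efficacy estimate. The added chance of an undetected pregnancy cannot be estimated from the documents.

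**What to change.** Keep the limit in Section 4.3 and carry it into the schedule:

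- In Sections 6.2.3 and 6.5.8, state that the baseline pregnancy test is done on Day -1 within 24 hours before dosing, or is repeated on Day 1 before intake if the last negative test is older than that.
- Add the conditional pre-dose test to the Day 1 list in Section 6.3.4 and as a footnoted Day 1 cell in Table 6.
- Record the date and time of the last negative test beside the dosing time on the administration form.

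The cost is wording in three sections, one table cell and one form field, processed as an amendment under Section 12 with the approvals required there. At most one urine test per woman is moved or repeated, about 42 to 106 tests under the assumption above, with a test the sites already use. If the baseline test is timed correctly, the count stays at five; a Day 1 test for every woman would make it six. A woman found pregnant on Day 1 is not dosed and is offered alternative treatment, as Section 14.3 already provides.

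If enrolment has closed, the sponsor can still compare test dates with dosing dates and apply one deviation rule to all women.
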